11 STUDY ADMINISTRATION

11.1 Ethics

11.1.1 Institutional Review Board

This protocol will be reviewed by the institutional review boards of the participating institutions,

11.1.2 Ethical Conduct of the Study

This research will be carried out in accordance with the protocol, US Code of Federal Regulations, GCP, 21 CFR Parts 50 and 56, the ethical principles set forth in the Declaration of Helsinki, and the ICH harmonized tripartite guideline regarding GCP (E6 Consolidated Guidance, April 1996).

11.1.3 Subject Information and Consent

The purpose of the study, the procedures to be carried out and the potential hazards will be described to the subjects in non-technical terms. Subjects will be required to read, sign and date an ICF summarizing the discussion prior to Screening and will be assured that they may withdraw from the study at any time without jeopardizing their medical care.

Subjects will be given a copy of their ICF.

11.2 Termination of the Study

The Principal Investigator reserves the right to terminate the study in the interest of subject welfare. The Sponsor may terminate the study for administrative reasons.

11.3 Data Quality Assurance

The Principal Investigator will designate personnel responsible for implementing and maintaining quality assurance and quality control systems to ensure that the study is conducted, and that data are generated, documented and reported in compliance with the study protocol, GCP and Good Laboratory Practice requirements as well as applicable regulatory requirements and local laws, rules and regulations relating to the conduct of the clinical study.

11.4 Direct Access to Source Data/Documents

The Principal Investigator will ensure that the Sponsor, IRB and domestic and foreign regulatory authorities will have direct access to all study sites, source data/documents, and reports for monitoring and auditing. If other study-related monitoring should be done by other parties, those parties will be required to sign a confidentiality agreement prior to any monitoring or auditing.

11.5 Study Device Supplies, Packaging and Labeling

The Sponsor will supply sufficient quantities of devices to allow completion of this study. Each subject in the "leva" arm will be provided with her own device and may retain the device at the end of the study. The Cost of goods value of the device is less than \$100. If

the subject does not already own an iPhone or android phone to run the *leva* software, they will be provided an alternative at no cost. It will be up to the discretion of the Sponsor if the alternative device needs to be returned to the study site or can be retained by the subject at the end of the study. Records will be made of the receipt and dispensing of devices supplied. This accountability record will be available for inspection at any time. At the completion of the study, the original accountability record will be available for review by the Sponsor upon request.

11.6 Data Handling and Record Keeping

All raw data generated in connection with this study, together with the final report, will be retained for at least 5 years after completion of the final report. These documents should be retained for a longer period however if required by the applicable regulatory requirements or by an agreement with the Sponsor. It is the responsibility of the Sponsor to inform the PI/Institution as to when these documents no longer need to be retained.

11.7 Publication Policy

All unpublished information given to the Principal Investigator by the Sponsor shall not be published or disclosed to a third party without the prior written consent of the Sponsor.

The data generated by this study are considered confidential information and the property of the Sponsor. This confidential information may be published only in collaboration with participating personnel from the Sponsor or upon Sponsor's written consent to publish the article.

NCT 03632447

A Prospective Randomized Efficacy Study Comparing a Pelvic Digital Health System Home Program of Pelvic Floor Muscle Exercise to Kegel Exercises in the Treatment of Stress-Predominant Urinary Incontinence

Statistical Analysis Plan

August 27, 2019

Statistical Analysis Plan

Secondary analysis of a Prospective, Nested, Randomized Efficacy Study Comparing a Pelvic Digital Health System Home Program of Pelvic Floor Muscle Exercise to Kegel Exercises in the Treatment of Stress-Predominant Urinary Incontinence (Renovia-05) –
Pilot/Feasibility Trail

Principal Investigator: Renovia Inc.

Prepared by: [name]

August 12, 2019

Table of Contents

1. Objectives.....	3
2. Design.....	3
3. Statistical analysis	3
3.1 Participant description.....	3
3.2 Feasibility	3
3.2.1 Feasibility of randomization.....	3
3.2.2. Feasibility of digital health platform	3
3.3 Compliance	4
3.4 8-week assessment	4
3.5 General statistical analysis guidelines.....	5
4. Additional comments.....	6
4.1 Reporting of statistical analyses	6
4.2 Additional analyses	6

1. Objectives

- Assess the feasibility of a randomized trial to test the efficacy of using a novel intravaginal system (leva[®] Plus Pelvic Digital Health System) to perform pelvic floor muscle exercises (PFME) compared to a Kegel exercise home program in women with stress-predominant urinary incontinence (SUI)
- Assess any technical issues with the digital aspect of the leva[®] Plus Pelvic Digital Health System
- Evaluate compliance with exercises in the leva[®] Plus Pelvic Digital Health System arm of the study

2. Design

The initial randomized study was ended early due to technical difficulties. This will be analyzed as a pilot/feasibility trial. Details about the randomized controlled trial study design and study visits can be found in the protocol, Renovia-05 (Sponsor: Renovia Inc.)

The study enrolled 60 women, randomized into the two initial arms (30 women per arm) and followed participants for 8 weeks.

3. Statistical analysis

3.1 Participant description

Baseline characteristics will include demographics (i.e. participant age, race, other measures of SES) and medical history (i.e. gravidity, parity, history of abdominal surgery) as reported on the baseline questionnaires. In addition, the results of the initial exam assessing urinary incontinence (including voiding diary, Pelvic Organ Prolapse assessment (POP-Q), PFDx device assessment) and the results of the questionnaires administered (PFDI, PISQ-IR, McGill Pain Questionnaire, SESPPFE, PGI-S, PGI-I, WHODAS, PFIQ) will be reported for both groups. Available scoring for all validated measures will be used.

3.2 Feasibility

Two aspect of feasibility will be assessed.

3.2.1 Feasibility of randomization

Participant flow will be described in a flow diagram. If available, the flow diagram will describe the number of potential participants approached and the number of participants consented and randomized.

3.2.2. Feasibility of digital health platform

In the leva[®] Plus Pelvic Digital Health System, the following will be described:

- Number of calls made for technical issues
- If available, categories of technical issues, as well as time since randomization

- Comparison of demographics of participants who called for technical issues vs. participants who did not call for technical issues
-
- Comparison of primary study outcomes of participants who called for technical issues vs. participants who did not call for technical issues

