- At 6- and 12- months they will participate in validated questionnaires (see chart) by phone and email or mail, in addition to reporting what (if any) additional therapies they have undergone for treatment of stress urinary incontinence at 6 months and 12 months after baseline.
- The third party research center will provide a single phone call to the subjects receiving the leva plus to ensure the device is functioning properly. If there are questions regarding the device function, a conference call will be undertaken to allow the subject to trouble-shoot device function with the sponsor technical specialist. The sponsor will at no time possess protected health information (PHI)

VISIT CONTENT

At week 4 all study participants will return to the office to undergo a PFDx evaluation of pelvic floor muscle function and complete and return the following questionnaires:

- a. PFDI
- b. PISQ-IR
- c. McGill Pain Questionnaire
- d. SESPPFE
- e. Patient Global Impression of Severity and improvement (PGI-S, PGI-I) Scale
- f. WHODAS
- g. PFIQ

At week 8 all study participants in both arms will return to the clinic for the PFDx device evaluation of pelvic floor muscle function and physical examination including a POP-Q and Brinks score, and the following questionnaires:

- a) PFDI
- b) PISQ-IR
- c) McGill Pain Questionnaire
- d) SESPPFE

- e) PGI-S and PGI-I
- f) WHODAS
- g) PFIQ
- h) Attestation of 80% or greater compliance with exercises twice daily as per protocol

The 6 and 12 months follow-up by phone and email or mail will include:

- i) PFDI
- j) PISQ-IR
- k) McGill Pain Questionnaire
- l) SESPPFE
- m) PGI-S and PGI-I
- n) WHODAS
- o) PFIQ

PFDx device pelvic floor muscle evaluation for both study arms will include:

- Baseline pelvic floor muscle vaginal angle (at rest)
- Pelvic floor muscle vaginal angle with Valsalva
- Pelvic floor muscle angle with relaxation
- Pelvic floor muscle angle with muscle contraction
- Number of repetitions of contraction in 15 seconds;
- Maximum time a subject can sustain a pelvic floor muscle contraction.

This evaluation will be conducted using the PFDx device placed in the vagina by the subject and conducted by study staff using an automated measurement protocol.

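### The technical-issues objective is measured only by calls, which captures help-seeking: unreported failures go uncounted and fall in the comparison group

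*SAP*

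**What the plan says.** The second objective in SAP section 1 reads, in part, "Assess any technical issues with the digital aspect of the" system under study. SAP section 2 gives the background: "The initial randomized study was ended early due to technical difficulties".

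SAP 3.2.2 turns the objective into four descriptive items for the leva arm:

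- a count, given as "Number of calls made for technical issues";
- the kinds of issue and when they arose after randomization, but only where such records exist;
- a demographic comparison of callers with non-callers;
- an outcome comparison on the same split, given as "Comparison of primary study outcomes of participants who called for technical issues vs. participants who did not call for technical issues".

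No other measure of device or app failure is named there.

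The protocol describes further places where a failure could come to light:

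- **Function check (8.1, Leva study arm).** Besides directing leva women to the sponsor's support team with technical problems, the protocol says a third-party research center "will provide a single phone call to the subjects receiving the leva plus to ensure the device is functioning properly". Questions about device function lead to a conference call with a sponsor technical specialist.
- **Withdrawal (8.3.3).** Inability to use the device is a possible reason for withdrawal.
- **Device data (8.4.2).** The device transmits training data to a database. SAP 3.3 uses device data only to check self-reported compliance.

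**The concern.** The objective concerns technical issues, while the measure and both groupings concern calls. The two agree only if nearly every woman with a problem called about it. A woman who met a fault and gave up quietly is not counted, and she is compared with callers as part of the other group.

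Two results are exposed. The first is how many of the 30 leva women were affected, which bears on whether the platform is ready for a full trial. The second is the SAP's only analysis relating technical issues to outcome. If the non-callers include women with failures, that contrast no longer compares women with and without an issue. The efficacy comparison between the randomized arms is not touched.

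**Working it through.** **1. The passages side by side.** The plan gives no figure on this point to reproduce, so the first check is of definitions.

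- The scope in SAP 1 is any technical issue. The only count named in SAP 3.2.2 is of calls.
- The item on categories and timing might draw on other records, but it names no source, is conditional on availability, and does not define the groups.
- Both comparisons are called versus did not call.
- SAP 3.2.2 does not say whether a fault found at the outbound function check, or the conference call that follows, makes the woman a caller.

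An unreported failure therefore contributes nothing to the count and falls in the comparison group.

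**2. How large the effect could be.** These figures are illustrative.

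Inputs: N = 30 leva women (SAP 2). Assumed: a share f with a failure, 20% to 60%; a share c of those who call, 25% to 75%; women without a failure do not call. For outcomes, assume 50% success without and 30% with a failure. These two percentages are borrowed from the between-arm assumption in Protocol 10.1.1 (30% success, 20-point difference); the documents do not apply them to technical issues.

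Formulas:
- callers = N × f × c
- silent failures = N × f × (1 − c)
- non-callers = N − callers
- silent share of non-callers = silent failures / non-callers
- observed difference, non-callers minus callers = 20 × (1 − silent share), in points, if calling is unrelated to outcome

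| f | c | Callers (% of 30) | Silent / non-callers | Observed difference |
|---|---|---|---|---|
| 20% | 75% | 4.5 (15%) | 1.5 / 25.5 = 6% | 18.8 |
| 20% | 50% | 3 (10%) | 3 / 27 = 11% | 17.8 |
| 20% | 25% | 1.5 (5%) | 4.5 / 28.5 = 16% | 16.8 |
| 40% | 75% | 9 (30%) | 3 / 21 = 14% | 17.1 |
| 40% | 50% | 6 (20%) | 6 / 24 = 25% | 15.0 |
| 40% | 25% | 3 (10%) | 9 / 27 = 33% | 13.3 |
| 60% | 75% | 13.5 (45%) | 4.5 / 16.5 = 27% | 14.5 |
| 60% | 50% | 9 (30%) | 9 / 21 = 43% | 11.4 |
| 60% | 25% | 4.5 (15%) | 13.5 / 25.5 = 53% | 9.4 |

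Fractions are expected numbers. If every affected woman calls (c = 100%), the silent share is 0 and the difference is the full 20 points: the problem disappears.

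**3. Selective calling.** Suppose half of the affected women call and are helped to 50% success, while silent failures reach 10%. Affected women then average 30%, so the true difference is still 20 points. With f = 40%, non-callers show (6 × 10% + 18 × 50%) / 24 = 40%, against 50% in callers. The sign has reversed, by 10 points. The same calculation gives 4 points at f = 20% and 17 points at f = 60%.

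**4. Precision.** With 6 callers at 30% and 24 non-callers at 45%, the standard error is √(0.30 × 0.70 / 6 + 0.45 × 0.55 / 24) = 0.213. The 95% interval is about ±42 points, far wider than the 5-point dilution in that row.

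**The case against.** The strongest reply is that the SAP says what it measures. It labels the group as women who did not call, which is accurate, and it never describes them as free of problems. The items are descriptive, and SAP 3.5 already asks for caution in reporting the primary analysis. This stands: the error arises only if not calling is read as having no issue. A reader could take the SAP to be making that classification, but its text does not. The risk of that reading remains, because no other SAP analysis relates technical issues to outcome.

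A reader might also infer that the plan counts events only, so that one woman calling six times cannot be told from six women calling once. That goes too far. Both comparisons need a count of women who called, and SAP 3.5 reports categorical variables as number and percentage of all women randomized to the group.

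Nor are the other sources wholly ignored. Protocol 8.3.3 has withdrawal reasons in the clinical report, SAP 3.2.1 provides a flow diagram, and SAP 3.3 reports how self-report agrees with device data, where missing sessions could appear as discordance. Faults found at the function check may be meant to count as calls, since SAP 3.2.2 does not exclude them. But none of these sources is brought into the technical-issue measure or its groups.

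The design also limits silent failure, through a named support contact, text messages six days a week and the proactive check. This lowers the likely size of the problem but does not settle it. SAP 4.2 permits additional analyses, but that discretion fixes no definition.

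**Conclusion.** The measure in SAP 3.2.2 is narrower than the objective in SAP 1. It records help-seeking, so the share of leva women with a technical issue can be understated and unreported failures fall in the comparison group.

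The size cannot be derived from the documents. Under the assumed ranges, silent failures make up 6% to 53% of non-callers and a 20-point outcome difference appears as 9 to 19 points. With near-complete calling there is no effect. Two stronger readings are not supported. One is that the comparison will reverse: this needs further assumptions about who calls and how they fare. The other is that failures of individual women's devices ended the trial: SAP 2 says only that there were technical difficulties.

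This is an inexpensive improvement to the measurement of a stated feasibility objective. With so few women the outcome comparison will be imprecise under either definition, so the main gain is in the count of women affected.

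**What to change.** In SAP 3.2.2:

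- Report the number and percentage of the 30 leva women with at least one recorded technical issue from any available source. The sources are support calls, problems found at the function-check call or its follow-up conference call, and withdrawals for inability to use the device where the recorded reason is technical.
- Use this variable to define the groups in both the demographic and the primary-outcome comparison.
- Keep the number of calls, and called versus did not call, as a secondary description of support use. State that not calling is not interpreted as having no technical issue.
- List women whose device data stop without a recorded reason separately, as possible cases. Leave them out of the issue group in the main comparison and move them into it only in a sensitivity analysis, because a data gap may be non-adherence.
- State which sources were actually available and used.

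The cost is SAP wording and some record review for 30 women, with no new data collection. SAP 3.3 already presumes that device data can be matched to participants. The limitation is that the protocol does not say function-check results were recorded, so that source may be incomplete.

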3.3 Compliance

Compliance will be assessed by participant report at the 8-week study visit. Participants who report performing the exercises at least 80% of the time will be considered compliant. Exercises using the leva[®] Plus Pelvic Digital Health System should be performed twice daily, for a total of 14 times per week; therefore, participants who perform the exercise at least 11 times per week will be considered compliant. Exercises in the control (Kegel) arm should be performed three times per day, for a total of 21 times per week; therefore, participants who perform the exercises 17 times per week will be considered compliant.

In addition, for participants in the leva[®] Plus Pelvic Digital Health System arm, self-report will be validated using data from the device. The distribution of concordance will be reported. Allowing for some error in reporting, reports within 1 exercise per week (over or under report) will be considered concordant. This may be altered based on the data, at which point the statistician and investigators may re-define concordance.

3.4 8-week assessment

The primary outcome, 8-week assessment, will be reported as described below. Efficacy will also be reported as both improvement on the PGI-I and no urinary distress on the PFDI-20. In addition, the results of the PFDI, PISQ-IR, McGill Pain Questionnaire, SESPPFE, WHODAS, PFIQ, PGI-S and clinical assessment of urinary incontinence (voiding diary, POP-Q, PFDx device assessment) will be reported.

Efficacy of leva[®] Plus Pelvic Digital Health System: Two definitions of efficacy will be reported as two “primary” outcomes. Both will be dichotomous (yes or no). Efficacy will be assessed at the 8-week visit and will be defined as: 1, improvement of symptoms, and 2, no urinary distress.

- “Improvement” will be defined as “much better” or “very much better” on the Patient Global Impression of Improvement (PGI-I) scale. Any other answers will be considered “No improvement”.
- “No urinary distress” will be defined as a raw score of 2 or less on all six indicators in the Pelvic Floor Disability Index (PFDI-20) Urinary Distress Inventory (UDI-6) subscale. Raw scores of greater than 2 will be considered reports of distress.

Both will be reported as the primary study outcome.

- **Pelvic Floor Disability Index (PFDI):** Obtain the mean value of all of the answered items within the corresponding scale (possible value 0 to 4) and then multiply by 25 to obtain the scale score (range 0 to 100). Missing items are dealt with by using the mean from answered items only. For the summary score, add the scores from the 3 scales together to obtain the summary score

(range 0 to 300). This can be reported as a continuous variable or may be categorized depending on distribution of the data. For the primary outcome, “No urinary distress” will be defined as a raw score of 2 or less on all six indicators in the UDI-6 subscale. Raw scores of greater than 2 will be considered reports of distress.

- **Pelvic Organ Prolapse/Urinary Incontinence Sexual Questionnaire (PISQ-IR):** Validated scoring available from Constantine, M.L., Pauls, R.N., Rogers, R.R. et al. *Int Urogynecol J* (2017) 28: 1901.
- **McGill Pain Questionnaire:** The level of pain for each word can be reported as None, Mild, Moderate, Severe. Collapsing of responses is also possible (pain vs. no pain, no/mild pain vs. moderate/severe pain). Reporting of the visual analogue scale will depend on data recording. Reports of pain location will need to be manually reviewed and categorized.
- **Self-Efficacy Scale for Practicing Pelvic Floor Exercises (SESPPFE):** Sum all of the scores to calculate total score for the scale. This can be reported as a continuous variable or may be categorized depending on distribution of the data.
- **Patient Global Impression of Improvement (PGI-I) Scale:** This is only a single question and will be dichotomized as improvement (“very much better” or “much better”) vs. no improvement (all other non-missing answers).
- **Patient Global Impression of Severity (PGI-S) Scale:** This is only a single question and can be reported as is.
- **World Health Organization Disability Assessment Schedule (WHODAS):** Two options are available for scoring the WHODAS. The first is a simple summary score as a continuous variable. The second option is to use the available coding provided by the WHO (http://apps.who.int/iris/bitstream/handle/10665/43974/9789241547598_eng.pdf;jsessionid=680B7F5F1FC5DE085FA4DCFD302F1176?sequence=1). A score of 17 or greater constitutes significant disability.
- **Pelvic Floor Impact Questionnaire (PFIQ):** Obtain the mean value for all of the answered items within the corresponding scale (possible value 0 – 3) and then multiply by (100/3) to obtain the scale score (range 0-100). Missing items are dealt with by using the mean from answered items only. To obtain a summary score, add the scores from the 3 scales together (range 0-300). This can be reported as a continuous variable or may be categorized depending on distribution of the data.
- **Pelvic Organ Prolapse assessment (POP-Q):** Assessment of pelvic organ prolapse will be conducted as medically directed. POP-Q stages may be reported as 0-IV, dichotomized as greater than or equal to Stage II vs. less than Stage II, or categorized depending on distribution of the data.
- **PFDx:** Assessment of baseline angle (rest angle), maximum angle (maximum squeeze), duration of pelvic floor lift (in seconds), valsalva angle (minimum angle), number of pelvic floor lift/relax repetitions in 15 seconds. All of these data will be reported as continuous.
- **Brink Score:** Scoring will be conducted as medically directed. All of the ratings will be summed and reported as a continuous variable.

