6 BACKGROUND

Pelvic floor muscle exercises (PFME), also known as Kegel exercises, are the first line conservative treatment for pelvic floor disorders, specifically stress urinary incontinence (SUI) within the urogynecology community. Studies have shown that performing PFME and/or pelvic floor physical therapy (PFPT) is the most effective non-invasive treatment for SUI. Some women have trouble identifying and contracting the correct muscles when performing PFME. The leva Pelvic Digital Health System™ is an innovative device that allows women to have real-time visual verification that PFME is performed correctly and consistently by guiding women through pelvic floor muscle lifting. The leva Pelvic Digital Health System™ also measures and records the results of every PFME session performed while using the device thus encouraging patient compliance. Data generated during exercise is transmitted to a safe, HIPAA compliant database in a cloud, from which an algorithm used to evaluate adherence can be used to provide automatic reminders and education via text message to encourage participation. In the proposed study we hypothesize that the leva Digital Health Platform:

- improves adherence to a long-term maintenance program of pelvic floor muscle exercises.
- leads to more significant improvements in pelvic floor muscle performance than a home PFME program.

There are other alternative biofeedback devices that are home-based and approved by the FDA, however these are expensive and may not be covered by insurance. There is no research to demonstrate that these devices are better than a PFME with or without supervision of a pelvic floor Physical Therapist. The *leva* device has a unique way of verifying muscle contraction that is not focused on strength, but rather vertical displacement with muscle contraction.

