8.4.2 Treatment Compliance

The *leva* device sends deidentified subject training and testing data to a secure, HIPAA compliant database, and subjects will receive periodic text messaging with training trips, reminders and motivational messages. Those in the Kegel control group will not be monitored for treatment compliance.

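### SAP 3.3 answers the leva-arm compliance objective by recalled self-report alone; a device-logged rate should be reported beside it

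*SAP*

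**What the plan says.** The third objective in SAP section 1 begins "Evaluate compliance with exercises in the leva" and concerns that arm only. SAP 3.3 then fixes the source of compliance status for both arms: "Compliance will be assessed by participant report at the 8-week study visit". The bar is 80% of prescribed exercises. For leva, prescribed twice daily, "participants who perform the exercise at least 11 times per week will be considered compliant"; for Kegel, prescribed three times daily, the figure is 17 a week.

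Device data enter once. For leva women, "self-report will be validated using data from the device", and the planned output is a distribution of concordance. The tolerance is that "reports within 1 exercise per week (over or under report) will be considered concordant", followed by "This may be altered based on the data, at which point the statistician and investigators may re-define concordance".

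The protocol supplies the context. Section 6 says the leva system "measures and records the results of every PFME session performed while using the device". Section 8.1 (leva arm) describes the week-8 report as recall with no diary, and says women are told that the system tracks them. The compensation text in section 8.1 adds $50 for those who attest to more than 80% completion. Section 8.4.2 says: "Those in the Kegel control group will not be monitored for treatment compliance".

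**The concern.** The leva arm has a session-level record of use, yet the plan answers the compliance objective from memory at week 8. The log can show that a report is wrong, but nothing in SAP 3.3 lets it change a woman's status or contribute a rate of its own. The planned outputs are therefore a self-reported proportion and a measure of agreement. Neither directly states what share of leva women reached the SAP's own cut according to the device.

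The payment may also matter. If the attestation that earns $50 is the report used in SAP 3.3, there is a reason to round upward. That link is an inference, because the case report form is not among the documents. At stake is how well a descriptive feasibility objective is answered; no efficacy result depends on it.

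**Working it through.** **1. The plan's cuts.** 0.80 × 14 = 11.2, rounded to 11 (11/14 = 78.6%). 0.80 × 21 = 16.8, rounded to 17 (17/21 = 81.0%). Both reproduce. Over 8 weeks the leva cut is 11 × 8 = 88 of 14 × 8 = 112 sessions.

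**2. Is the cut of 11 already a device rule?** No. It follows from the sentence that makes participant report the source, and the same verb (perform) is used for the Kegel arm, which has no monitoring.

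**3. What the concordance check can and cannot show.** Take whole-number weekly counts from 0 to 14 for both report and log.
- Report 11 to 14 with log 0 to 10: 4 × 11 = 44 combinations, all counted as compliant. The ±1 rule flags 43 and passes one (report 11, log 10).
- Report 0 to 10 with log 11 to 14: 11 × 4 = 44 combinations, all counted as non-compliant. The rule flags 43 and passes one (report 10, log 11).

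The check therefore detects nearly every mismatch in status, but it also flags pairs with no mismatch. Report 14 with log 12 and report 12 with log 10 both differ by 2; the first pair is compliant on both measures and the second is not. A distribution of differences does not separate them. A full cross-tabulation of reported against logged counts would, but the SAP does not say which will be shown. The rule also needs a reported weekly count, and the week-8 attestation in protocol 8.1, worded as 80% or greater compliance, does not evidently provide one.

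**4. How far the two rates could differ.** The documents give no error rates, so these values are assumed. Suppose 18 of 30 reach the cut by device (60%, exact 95% CI 40.6% to 77.3%). Let a be the number of the other 12 who report compliance, and b the number of the 18 who do not report it or miss the visit. The self-reported rate is (18 + a − b)/30.

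| a | b | Self-reported rate |
|---|---|---|
| 0 | 0 | 18/30 = 60% |
| 3 | 0 | 21/30 = 70% |
| 6 | 0 | 24/30 = 80% |
| 3 | 3 | 18/30 = 60% |
| 0 | 3 | 15/30 = 50% |

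Each woman moves the rate by 1/30 = 3.3 points. The gap can have either sign, and it can be zero while six women are misclassified (a = b = 3).

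**5. The log can be wrong too.** Protocol 8.2 describes leva Plus as still under development, and SAP section 2 says the trial stopped early because of technical problems. Lost sessions lower a logged rate. A woman doing 12 a week (96 sessions) falls below 88 if 9 are lost (87 left; 9/96 = 9.4%). One doing all 112 falls below only if 25 are lost (87 left; 25/112 = 22.3%).

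**6. Bounds for unusable logs (illustrative).**
- 3 unusable, 17 of the other 27 compliant: 17/30 = 56.7% to 20/30 = 66.7%.
- 9 unusable, 15 of the other 21 compliant: 15/30 = 50.0% to 24/30 = 80.0%.

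**The case against.** The strongest reply is that the SAP already uses the device data. Validation needs each woman's logged count, the ±1 rule flags 43 of the 44 combinations with a wrongly compliant status, and a fully tabulated concordance distribution could nearly give the device share. Self-report is the only measure common to both arms, so one definition with validation where possible is coherent. SAP 4.2 also permits further analyses. In a trial stopped for technical problems, the log may be the weaker source.

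Much of this stands. It would be too strong to say that the device share cannot be recovered; that depends on a table format the SAP leaves open. Self-report is right for describing the two arms side by side, and a device rate restricted to usable logs should not become the headline. Such a rate would drop the women whose devices failed and depart from the denominator in SAP 3.5, which is every woman randomized to the arm.

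What does not stand is that this fills the gap. Permission to add analyses is not a plan, and the objective concerns the leva arm alone, where a second measure exists. The clause allowing concordance to be re-defined is minor: it is disclosed, and no compliance status or test depends on it.

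A reader might also infer that self-report inflates leva compliance. The documents do not show this. They give no over-report rate, SAP 3.3 itself allows for error both ways, and the women knew they were tracked.

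**Conclusion.** The point holds as a low-priority improvement. SAP 3.3 settles leva-arm compliance by recalled self-report, plans no device-based rate, and leaves a woman with a contradicting log counted as compliant. No figure in the SAP is wrong.

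The size of the effect is unknown. The 60% example and the values of a and b are assumptions; the combination counts only describe which mismatches are possible. The documents support neither a claim that compliance will be overstated nor a claim that the log is the true value. They support reporting both measures, each with its limits visible. The efficacy outcomes rest on the PGI-I and the UDI-6 and are untouched.

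**What to change.** For the leva arm, add to SAP 3.3, beside the self-reported rate and with neither displacing the other:

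- the proportion of all 30 randomized women averaging at least 11 logged sessions a week. Because no visit window is given, use each woman's own days from baseline to week 8 (88 sessions if that is exactly 56 days);
- the number of missing or faulty logs, with bounds counting them first as all non-compliant and then as all compliant. Define missing and faulty before analysis, keeping a device that was not used (a true low count) apart from a record that was lost. The technical-issue calls in SAP 3.2.2 can help, though a fault need not produce a call;
- the percentage of prescribed sessions logged, as a continuous measure;
- a 2x2 table of self-reported against device status at the same cut, with the number missing on either measure.

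Keep self-report for any description across arms, because Kegel women are not monitored. Keep the ±1 rule as stated if weekly counts were collected, and label any later re-definition post hoc.

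The cost is some SAP wording, a rule for faulty logs and one or two tables. No new data are needed, since the planned concordance check already requires the logged counts. The downsides are that the device rate may be lower than self-report, lost sessions may bias it downward, and the bounds may be wide.
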